Statistical analysis for the imaging primary endpoints will initially estimate the slope between 0 and 3 months (no study drug) and the slope across 3, 9 and 15 months (sulindac treatment) separately for each woman. The slope between 0 and 3 months is the difference between the two measurements (divided by the time interval), while the slope while on sulindac will be estimated using linear regression analysis (to allow for the possibility of slight variability in the timing of the measurements). Preliminary analysis will assess whether the pattern of change with sulindac treatment is linear. Mean slopes and 95% confidence intervals will be estimated for the baseline (no study drug) and sulindac treatment periods. Comparisons of the mean slope with and without sulindac will be performed using a paired t test since the imaging endpoints as Fra50 from FWR-MRI (Aim 1 and primary trial endpoint) and ADC from DW-MRI (Aim 2) will be restricted to images from the unaffected, contralateral breast. The BPI-SF measure of past-week worst pain is a discrete, ordinal value. Statistical analysis will proceed using a proportional odds model with a robust variance estimate to account for potential correlation among measures in the same woman. The independent variable will be time; differences in the values observed during the baseline and sulindac treatment periods will be estimated using a linear contrast of the estimated coefficients. Adjustment for the inflated alpha level due to the use of three primary study endpoints (FWR-MRI, DW-MRI, and BPI-SF) will be performed using the Bonferroni correction. The incidence of any  $\geq$  grade 2 hypertensive adverse events will be compared during the baseline and sulindac treatment periods using McNemar's test. Since this is a safety endpoint, no multiple comparisons adjustment of the alpha level will be performed.

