## **27.2 Sample size justification for primary aims and trial endpoint**

Our TOTAL sample size ensures adequate power to test all *three* primary aims. For the observational group, a sample size of 60 with complete follow-up matches our intervention arm and ensures an

adequate comparison group size to test unknown effects of AIs on BD as measured by fat/water-MRI as well as to assess the two additional endpoints of pain and hypertension.

To justify the sample size for the sulindac intervention, we considered the primary trial endpoint, which is to compare the difference in the slope of the FWR-MRI-derived log (Fra50) between the baseline and sulindac treatment periods. Based on previous findings using mammographic density measures in randomized trials of AI (see Table 1), we assume there will be no more than a 5% change during the 12 month on intervention study and only a 1-2 % difference between the two baseline periods (observational period in the intervention arm of 3 months) due to between measurement variability. For the sulindac treated group, we assume an initial sample size of 100 women and allow the possibility of up to 20% dropout for the end of intervention follow-up measurement. This results in at least 80 evaluable women.

With 80 women we will be able to detect a decrease of 0.368 standard deviation (SD) units in the slope while on sulindac treatment versus the baseline slope with 80% statistical power, assuming a two-sided  $\alpha$  of 0.017 (*adjusted for multiple comparisons*). To estimate what this change would be in relation to BD, we used the relationship between BD and log(Fra50) from our previous study. Based on an analysis of our cross-sectional data, the estimated SD of log(Fra50) is 2.40. Thus, a decrease of 0.368 SD units corresponds to a change of -0.883 (-0.368\*1.40). Based on the regression line, this is equivalent to a 4% average decrease in BD as determined by CAD assisted BD by mammography. Note, that while this is the effect size that we are able to detect, enthusiasm for the potential to move sulindac forward for an efficacy trial would be much greater with average decreases of more than double that of projected age related change. Thus, the study is well powered to detect even small differences. However, effect sizes < 8% average decrease in Fra50 will not be considered highly impactful in interpreting the results from a clinical perspective given the average age-related decline in BD is 1-3%.

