### **27.3 Conduct of and Justification for Planned Futility Analysis**

As discussed in the funded grant submission, we would like to limit women's exposure to agents that are unlikely to effect change in the breast in a clinically meaningful way. Therefore, we will include a futility analysis for the primary trial endpoint of FWR log(Fra50) after 40 women have reached the 15-month endpoint. This analysis is for futility only, so it will not affect the overall  $\alpha$  level. Briefly, the observed results from these women will be used to compute the difference between the slope during sulindac treatment versus the baseline period. Predicted results for future participants will be generated from a log-normal distribution with the observed mean and SD. One thousand bootstrap samples with a sample size of 80 women will be generated to estimate conditional power. The study will continue if conditional power  $\geq 80\%$  is met. If we fail to pass futility, we plan to **stop accrual to the study and suspend study agent for women who are active**. We plan to follow all women who initiated trial agent to their next imaging endpoint (9 or 15 months, whichever comes first). Considering a dropout rate of 10% by 9 months and 20% by 15 months, and a planned accrual rate of 5 participants/month starting in month 6 of funding, we expect to have 40 evaluable participants followed to 15 months by approximately 3 years; by then, ~90 participants will have completed 9-month measures, and ~100 will have initiated the trial.

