In consultation with NCI, concern was raised that prior studies of AIs showing no effects of AIs on BD were based on mammography and not the more sensitive MRI method under investigation. As such, an observational (non-randomized) control group comprised of BC patients stable on an AI was included specifically to monitor for AI effect on BD using the MRD method.

Initially, the target sample size was reduced to 75 and 60 in the intervention and observation groups, respectively. A previously planned futility analysis of SUL effect on MRD after 40 participants completed 12 months of intervention was changed to the primary analysis on limited resources and slow accrual. Patients consented to banking tissue biopsies for future biomarker studies.

Modified Study Hypotheses: Because of the modification to the study design, the study hypotheses were modified as follows:

Primary

SUL 150 mg BID for 12 months will decrease MRD in postmenopausal women taking aromatase inhibitor therapy.

- a. As a sensitivity analysis of this primary hypothesis, per-study analysis described below will also be performed using only subjects who are adherent with study protocols (adherence is defined as having taken at least 80% of study agent).
- b. As a sensitivity analysis of this primary hypothesis, per-study analysis for primary hypothesis will also be performed using only those subjects with baseline BD $\geq 15\%$.

Secondary

SUL 150 mg BID for 12 months will be well tolerated and grade 3 adverse events will not exceed 10% and patients who drop out secondary to adverse events will not exceed 10%. *With low sample size of 40, only when there are no grade 3 AE or drop out secondary to AEs, can say it will not exceed 10% (point estimate is 0% with 95% Blyth-Casella-Still CI (0-7.78%).*

Reportable Outcomes

1. Change in BD from baseline at 6 and 12 months by MRD in postmenopausal women receiving AI for treatment of breast cancer and 95% confidence interval will be reported separately for:
 - a. participants in the sulindac group who started sulindac and who had at least one MRD measure on intervention,
 - b. participants enrolled and started in the observation arm with at least one MRD measure post baseline,
 - c. participants adherent to SUL intervention (same caveats as a), and

- d. in both arms but reported separately for participants with baseline BD $\geq 15\%$ (same respective caveats as a and b).

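### The 80% power claim in protocol 27.2 does not describe the primary breast density analysis, which the SAP moves to 40 completers under a different model with no alpha, power or precision stated

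*SAP*

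**What the plan says.** Protocol 27.2 assumes 100 women with up to 20% dropout, leaving 80 evaluable: "With 80 women we will be able to detect a decrease of 0.368 standard deviation (SD) units in the slope while on sulindac treatment", with 80% power at two-sided alpha 0.017. It converts the effect to density ("this is equivalent to a 4% average decrease in BD", on computer-assisted mammography) and concludes: "Thus, the study is well powered to detect even small differences". It adds that an effect below an "8% average decrease in Fra50 will not be considered highly impactful in interpreting the results from a clinical perspective".

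The test behind the power statement is in protocol 27.1: "Comparisons of the mean slope with and without sulindac will be performed using a paired t test". The alpha of 0.017 comes from a Bonferroni correction in the same section: "Adjustment for the inflated alpha level due to the use of three primary study endpoints (FWR-MRI, DW-MRI, and BPI-SF".

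Protocol 27.3 plans one look: "we will include a futility analysis for the primary trial endpoint of FWR log(Fra50) after 40 women have reached the 15-month endpoint". It describes that look as for futility only.

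The SAP (last modified 11/4/2019) says in its account of the modifications: "A previously planned futility analysis of SUL effect on MRD after 40 participants completed 12 months of intervention was changed to the primary analysis". The reasons given are limited resources and slow accrual. Its Final Data Analysis Plan replaces the paired slope test with a linear mixed model of log breast density, adjusted for baseline density. The primary analysis set is women who start sulindac, and Reportable Outcome 1a requires at least one on-treatment scan. Confidence intervals of 95% are promised for months 6 and 12. The only numerical statement tied to a sample of 40 concerns grade 3 adverse events and dropouts due to adverse events.

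**The concern.** The two documents give the same 40-woman look different roles. In the protocol it is a stopping check on the way to 80 women. In the SAP it is the primary analysis. The protocol carries wording dated January 2021 (14.2.2 and section 20), so it was edited after the SAP, yet 27.2 and 27.3 still describe the 80-woman plan.

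Nothing replaces the lost justification. For breast density the SAP says that pooling the groups narrows the interval and that baseline adjustment helps power, but it puts no number on either. Alpha is also unsettled: the protocol divides it over three endpoints, the SAP's modified goals number two, and its modified hypotheses contain one primary.

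What is at stake is how a null result is read. Someone relying on 27.2 would take an interval that includes zero as coming from a study with 80% power for about a 4% decrease in density.

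**Working it through.** **Inputs.** Standardized effect d = 0.368, n = 80, two-sided alpha 0.017 and power 80% (protocol 27.2). Paired t test (protocol 27.1). n = 40 completers (SAP). Alpha 0.05 is my assumption for the SAP, from its 95% intervals and single primary hypothesis; the SAP does not state it.

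**Formula.** Power of a paired t test from the noncentral t distribution with n − 1 degrees of freedom and noncentrality d√n, against the critical value t(1 − α/2, n − 1).

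**Step 1: the protocol's figure.** n = 80: noncentrality 0.368 × √80 = 3.29, critical value 2.44, power 80.1%. Enrolment: 80 / (1 − 0.20) = 100. Both reproduce.

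**Step 2: the same test and effect with fewer women.**

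| n | Power, α = 0.05 | Power, α = 0.017 | 80%-power effect, α = 0.05 | 80%-power effect, α = 0.017 |
|---|---|---|---|---|
| 80 | 90.2% | 80.1% | 0.317 SD | 0.368 SD |
| 75 | 88.2% | 77.0% | 0.328 SD | 0.380 SD |
| 60 | 80.1% | 65.4% | 0.368 SD | 0.427 SD |
| 50 | 72.3% | 55.6% | 0.404 SD | 0.470 SD |
| 40 | 62.2% | 44.3% | 0.454 SD | 0.530 SD |

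At n = 40 the noncentrality is 0.368 × √40 = 2.33, against critical values of 2.02 (0.05) and 2.49 (0.017). The rows for 50 and 60 are assumed sizes, shown because the analysed number may exceed 40. The 75 is the SAP's intermediate target, taken here as if all were evaluable.

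**Step 3: a check inside the protocol.** Section 27.4, on the biopsy comparisons, says that 40 women detect 0.45 SD with 80% power at two-sided 0.05. The table gives 0.454 SD. The protocol's own figure for 40 women is thus larger than the 0.368 SD claimed in 27.2.

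**Step 4: what an interval that includes zero excludes.** The 95% half-width on this test is t(0.975, n − 1)/√n, or 0.320 SD at n = 40 and 0.223 SD at n = 80. An interval covers both 0 and 0.368 SD when the estimated decrease lies between 0.368 minus the half-width and the half-width itself. That is 0.048 to 0.320 SD at n = 40, and 0.145 to 0.223 SD at n = 80.

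**Step 5: why this is not the SAP's precision.** The only SD given, 2.40 for log(Fra50), is cross-sectional. As a simplification, take a difference of two measurements with repeat correlation r, so that the SD of change is 2.40 × √(2(1 − r)). Hold the absolute effect at 0.368 × 2.40 = 0.883 (27.2 prints the multiplier as 1.40, but only 2.40 gives 0.883). At n = 40:

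- r = 0.5: SD 2.40, d = 0.368, power 62% (0.05) or 44% (0.017).
- r = 0.8: SD 1.52, d = 0.582, power 95% or 88%.
- r = 0.9: SD 1.07, d = 0.823, power over 99% at both.

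The documents give no r, so these are assumed values.

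**The case against.** The strongest reply is that the 40-woman figures belong to a test the SAP has abandoned. They concern a paired difference in slopes of log(Fra50). The SAP estimates change from baseline in log density with a baseline-adjusted mixed model. Step 5 shows that a high repeat correlation could remove the shortfall in absolute terms, and protocol 6.1 reports between-measure variability of about 1–2% for the MRI method, which points that way without giving r. This stands. A reader might infer that the planned primary analysis has 62% or 44% power. The documents do not support that, because its precision cannot be computed from them.

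The 44% figure is also the weaker of the two. With one primary hypothesis and 95% intervals, two-sided 0.05 is the natural reading of the SAP, although it never says that the Bonferroni share has lapsed.

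The SAP is also open about its limits: it calls the trial a single-arm feasibility study, and its reported intervals will show their own width. Protocol 27.2 discounts effects below 8%. If 8% is taken as twice 0.368 SD, or 0.736 SD (an assumption, since the 8% is stated on Fra50 and the 4% on breast density), 40 women still give 99.5% (0.05) or 98% (0.017) on the protocol's test. It would therefore be wrong to infer that the trial cannot detect an effect the investigators would act on. Finally, the January 2021 text concerns moving samples and does not re-endorse 27.2.

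None of this removes the conflict. The protocol still asserts 80% power and a futility-only look, and the SAP contradicts the second and leaves the first without a basis.

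**Conclusion.** The point holds as a failure to reconcile the two documents, together with an omission in the SAP. The power arithmetic in 27.2 is correct on its inputs, so it would be wrong to read this as a miscalculated sample size.

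The stated 80% does not describe the analysis that the SAP makes primary. On the protocol's own standardized test, power for 0.368 SD falls to about 62% or 44% at 40 women, and the effect detectable with 80% power rises to 0.454 or 0.530 SD. These figures hold d, the test and n = 40 fixed, and serve only to show that the claim does not transfer. Confidence in the conflict is high. Confidence in the size of any loss under the mixed model is low, because the within-woman SD and the analysed n are both missing. On the protocol's test the loss concerns effects near the planned 0.368 SD, with little loss at twice that size.

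**What to change.** 1. **Protocol 27.2 and 27.3.** Keep the 80-woman calculation as the original plan, but mark it and the futility-only role of the 40-woman look as superseded. Reconcile both with the SAP. Remove or qualify the sentence that the study is well powered for small differences. Do not present 62% or 44% as the power of the planned analysis.
2. **SAP.** State the expected analysed n: 40 completers plus other starters with at least one on-treatment scan. State the alpha for the single primary breast density hypothesis, and whether the Bonferroni 0.017 still applies. Give the expected 95% CI half-width for 12-month change in log density at that n, with a sourced within-woman SD. The two pre-sulindac scans, three months apart, can supply one without using on-treatment data. Show a range, since change over 12 months may vary more than change over three. As a guide, for a simple mean change in 40 women the half-width is 0.320 times that SD.
3. **Interpretation.** Say that an interval including zero need not exclude the originally planned 0.368 SD, beside the existing statement that effects below 8% are not highly impactful.

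The cost is a protocol revision, which needs human-subjects approval before implementation (protocol 28.2), and possibly a less favourable stated sensitivity. No further patients are needed, since accrual is concluded (protocol 4.4).

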- 2. For the SUL intervention group, change in BD measured by MRD and 95% confidence interval will be reported for during the 3-month observation period.
- 3. For the SUL intervention group, change in WOMAC, BPI and FACT-G measures and 95% confidence interval will be reported for participants who *initiated* intervention with SUL 150 mg BID at 3, 6 and 12 months. Separately, change for participants with elevated baseline pain levels for BPI and WOMAC or lower quality of life for FACT-G will be reported. [Specifically, for BPI worst pain, severity, and interference-elevated pain will be defined as a score ≥ 2 . For WOMAC, elevated pain will be defined as subscale and total scores above the arm-specific medians will be calculated; for FACT-G a lower quality of life will be defined as subscale and total scores below the median for all participants].
- 4. For the observation group, change in WOMAC, BPI and FACT-G at 6 and 12 months and 95% confidence interval will be reported. Separately, change for participants with elevated baseline pain levels for BPI and WOMAC or lower quality of life for FACT-G will be reported (as defined above). Secondarily, report on change in individual questions and measurement subscales.
- 5. For the sulindac group, the proportion of patients agreeing to core needle biopsy at baseline and repeat at 6 months.

Final Data Analysis Plan

Hypothesis Testing: For the final analysis, all baseline characteristics will be summarized with appropriate descriptive statistics.

Linear mixed effects model for longitudinal data will be used for testing the primary hypotheses. The fixed effects of the model will include individual groups (SUL and observation) as well as the combined group (SUL and observation [pooled]) for comparison purposes and each visit (baseline, month 6 and month 12) and for the pooled analysis, an interaction between group and visit. In theory, pooling data for the two groups will allow us to generate a more precise estimate of BD change. *Pooling data together allows us generate a narrower 95% CI of estimated BD change.*

Baseline BD, age, as well as important prognostic variables such BMI will be used as covariates. The model will include a random intercept at the subject level to account for correlations due to the repeated measurements from the same subjects. The dependence structure for longitudinal data from

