the same subject will be selected with the Akaike Information Criterion. Log-transformed BD at each time point will be used as the outcome with adjustment for log-transformed baseline BD to improve efficiency and hence power for modeling % change in BD directly.

Note: *There is no prespecified plan to conduct a statistical test comparing change in BD between the two study groups.*

Only subjects who start SUL intervention will be included in the primary analysis. This allows us to evaluate the effect of SUL in those individuals who start intervention. 95% confidence intervals of BD change at month 6 and month 12 in the SUL group will be reported.

There are few patients whose MRD could not be obtained because of image artifact. As a sensitivity analysis, multiple imputation will be used to impute all missing MRD using patients' baseline information such as age, race, BMI, cancer stage, chemotherapy and radiation therapy information, AI use and NSAID use. Ten imputed datasets will be generated and all estimates about BD% change will be constructed using Rubin's rule. All analysis for primary hypothesis will be repeated among a subgroup of patients whose baseline BD $\geq 15\%$ and further using only SUL patients with $>80\%$ drug adherence.

For secondary hypothesis, all adverse events and severe adverse events from patients in the SUL group will be reported. The rate of patients with grade 3 or higher adverse events will be reported along with 95% Blyth-Casella-Still confidence interval.

For Reportable Outcomes

The linear mixed effect model fitted for the primary analysis will also be used to estimate the BD% changes and 95% confidence intervals at month 6 and month 12 within the observational group.

As part of this analysis for reporting purposes, we will describe the comparability of the intervention and non-random observation arm, continuous characteristics will be compared among study arms using Welch's two-sample t-test. Categorical variables will be compared using Chi-square test and exact p-values based on simulations may be reported if there is data sparsity. Any differences will be reported.

Percentage change in BD during the 3-month observation period in the SUL group will be reported with its 95% confidence interval (*i.e.* % change as $[BD \text{ at the end of observation period} - BD \text{ at the beginning of observation period}] / BD \text{ at the beginning of observation period}$).

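### The SAP credits pooling the arms with a narrower confidence interval, but with a group-by-visit term pooling barely informs the sulindac change and mainly imposes a common variance, which can mis-calibrate the interval in either direction

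*SAP*

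**What the plan says.** All of the following is in the SAP, Final Data Analysis Plan.

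- Fixed effects under Hypothesis Testing cover "individual groups (SUL and observation) as well as the combined group (SUL and observation [pooled]) for comparison purposes", each visit (baseline, month 6, month 12) and, "for the pooled analysis, an interaction between group and visit".
- Two consecutive sentences then claim greater precision from pooling. The second reads "Pooling data together allows us generate a narrower 95% CI of estimated BD change". No width, SD or percentage is given.
- On variance, "The model will include a random intercept at the subject level", and the dependence structure for longitudinal data from "the same subject will be selected with the Akaike Information Criterion". Variance parameters by group are not mentioned.
- "Baseline BD, age, as well as important prognostic variables such BMI will be used as covariates". No covariate-by-group term is stated.
- On the primary result, "Only subjects who start SUL intervention will be included in the primary analysis", and "95% confidence intervals of BD change at month 6 and month 12 in the SUL group will be reported". The paragraph on reportable outcomes then says that the model fitted for the primary analysis will also supply the observation-arm changes.
- No test between the arms is planned.

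**The concern.** A group-by-visit interaction gives each arm its own mean at each visit. Observation women then say almost nothing about the mean change on sulindac. They enter its interval mainly through a shared residual and random-intercept variance. The precision claim therefore needs equal spread in the two arms, which the SAP neither states nor checks.

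Equal spread cannot be taken for granted. The arms are not randomized (Protocol section 17), many exclusions apply to the sulindac arm only (section 15.2), and dose reductions and drug holidays arise only on sulindac (section 24). None of this shows which arm varies more. It shows only that a common variance is a real assumption.

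The primary hypothesis will be judged on this interval in a small sample. If its source is left open, an analyst could choose between the joint and the sulindac-only interval after seeing both, and the SAP's text favours the narrower one.

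**Working it through.** **Plan's own figure.** The SAP gives no figure for the gain from pooling, so there is none to reproduce. The protocol's precision figure for this endpoint (section 27.2: 80 women, 0.368 SD, two-sided α 0.017, 80% power) does reproduce: a paired t test gives 80.1% power. It does not involve pooling.

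**Inputs.** Sulindac n₁ = 40, the number of 12-month completers that triggers the primary analysis (SAP, Study Modifications). Observation n₂ = 60, which is an assumption: 60 is a target in the SAP and the expected number of completers in Protocol section 27.1, not a count at the time of analysis. The ratio r of the sulindac SD of change to the observation SD is also an assumption, varied from 0.71 to 2, because the documents give neither SD.

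**Step 1: does the estimate itself change?** Random-intercept models (REML) with group, visit, their interaction, age and BMI were fitted to simulated 40/60 data, with and without the observation arm (40 simulated trials per setting).

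- Complete data: the 12-month sulindac estimates were identical (difference 0.000000).
- 15% of follow-up visits missing: they differed by at most about 0.002 log units, and the empirical SD of the estimate was unchanged to within 0.0001.
- The reported standard error did move. The ratio of joint to sulindac-only was about 1.01 at equal residual variances, 0.84 with the sulindac variance doubled and 1.26 with it halved.

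**Step 2: interval width.** For a mean change, the sulindac-only half-width is t(n₁−1)·s₁/√n₁. The common-variance half-width is t(n₁+n₂−2)·s_p/√n₁, where s_p² = [(n₁−1)s₁² + (n₂−1)s₂²]/(n₁+n₂−2). With s₂ = 1 and s₁ = r, the width ratio is approximately (1.984/2.023)·√[(39r² + 59)/98]/r.

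- r = 1: 0.981 × 1 = 0.981. Simulation gives 0.985, so the gain is about 1.5–2%.
- r² = 2: 0.981 × √(137/98)/1.414 = 0.981 × 0.836 = 0.82. Simulation gives 0.823.
- r² = 0.5: 0.981 × √(78.5/98)/0.707 = 0.981 × 1.266 = 1.24. Simulation gives 1.246.

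**Step 3: coverage of the nominal 95% sulindac interval, 40/60, by simulation.**

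| SD ratio r | Common variance | Sulindac-only variance |
|---|---|---|
| 0.71 | 98.6% | 95% |
| 1 | 95% | 95% |
| 1.25 | 91.7% | 95% |
| 1.5 | 89% | 95% |
| 2 | 85% | 95% |

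The error shrinks with fewer observation women: at r = 1.25, coverage is 92.9% with 30 of them. It also shrinks with more sulindac women: at 75/60 and r² = 2, coverage is 91.7%, against 89.9% at 40/60.

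**Step 4: dropping the interaction.** At 40/60 with equal variances the width ratio falls to 0.62. That interval is for a blend of the arms with sulindac weight 40/(40+60) = 40%, so it does not estimate the change on sulindac.

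**The case against.** Four points on the other side have weight.

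1. **The primary interval may never use the joint model.** The SAP names individual-group models first, labels the combined group as being for comparison, and restricts the primary analysis to women who start sulindac. On that reading no variance is borrowed. This stands as a possible reading. Against it, the model fitted for the primary analysis is also to yield observation-arm changes, which needs both arms in it. The text does not settle the matter.

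2. **Pooling is not worthless.** A reader might infer that it adds nothing at all. That goes too far: it adds degrees of freedom and, with missing visits, shares variance components. It also shares covariate slopes. In a simulated baseline-adjusted model (equal variances, 40/60, slope −0.4, change evaluated at the pooled baseline mean), the joint interval was 2% narrower with balanced baselines, 3% at an imbalance of 0.25 SD, 5% at 0.5 SD and 11% at 1 SD, with coverage of 95.0–95.4%. Apart from the degrees of freedom, this gain vanishes if change is evaluated at the sulindac arm's own covariate means. The SAP does not say which is used.

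3. **The direction is unknown.** A reader might infer that the primary interval is too narrow because response to a drug should vary more than no treatment. Neither document gives an SD that supports this. If sulindac women vary less, the common-variance interval is too wide. Coverage of 85% needs a fourfold variance ratio.

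4. **The combined-group estimate is not the primary hypothesis.** That is so, and reporting it does no harm if it is labelled for what it is.

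**Conclusion.** The precision claim is not supported as a general statement. With the interaction in the model, the sulindac change comes essentially from sulindac women. The dependable gain at 40/60 is about 1.5–2% of width and requires equal variances. Shared covariate slopes may add to it, depending on baseline imbalance and on where change is evaluated. Any other change in width reflects the common-variance assumption.

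The documents do not establish that the primary interval is wrong, or that it is too narrow. They leave its source open and give no arm-specific SD. If it comes from the joint model with one variance, coverage runs from about 98.6% to 85% over SD ratios from 0.71 to 2, under the assumed 40/60 split and simple t intervals for mean change. If it comes from sulindac women alone, the problem does not arise.

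**What to change.** State in the SAP that the month-6 and month-12 changes and 95% intervals for each arm come either from arm-specific models or from the joint model with group-specific variance parameters. In simulation, the sulindac arm's own variance held coverage at 95% at every ratio tried.

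Delete the two precision sentences, or limit them to the small gain available under equal variances. If the combined-group estimate is kept, label it descriptive and say that it does not estimate the change on sulindac.

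The cost is a sentence or two and one model option. The sulindac interval may be slightly wider: at equal variances the loss is the 1.5–2% shown above.
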